6.10.2.2.3. Duration of Response

The DOR is derived from data of patients who achieved response (CR or PR) and is defined as the time from the date of response achievement (the first observation of response before confirmation) to the date of objectively determined PD.

For the responders in the FAS population, the number of events and the DOR will be summarized by part and cohort.

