10.6. Efficacy

Efficacy data will be summarized by part and cohort using the FAS population. Efficacy data includes the objective response rate with confirmed partial response (PR) or complete response (CR), and the disease control rate with confirmed PR, CR, or stable disease (SD) as best overall response according to RECIST version 1.1. Progression-free survival and duration of response will also be included in efficacy data.

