6.10.2.2. Other efficacy outcomes

The overall survival (OS), the progression-free survival (PFS) and the duration of response (DOR) will be evaluated using the Kaplan-Meier method as described bellow.

For the FAS population, a listing of efficacy outcomes (i.e. BOR, OS, PFS and DOR) will be provided.

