6.10.2.2.2. Progression-free Survival

The PFS is defined as the time from the date of the first infusion of the study drug to the date of objectively determined PD or death from any cause, whichever is first. Censoring rules are described in [Table JGDK.6.1](#).

Table JGDK.6.1. Censoring rules

Situation	Date of Progression or Censoring	Outcome
-----------	----------------------------------	---------

Situation	Date of Progression or Censoring	Outcome
No baseline tumor assessments	Date of the first infusion of the study drug	Censored
Progression documented between scheduled visits	Earliest of the following dates: 
 • Date of radiological assessment showing new lesion (if progression is based on new lesion) • Date of last radiological assessment of measured lesions (if progression is based on increase in sum of measured lesions) 	Progressed
No progression	Date of last radiological assessment of measured lesions	Censored
discontinuation for undocumented progression	Date of last radiological assessment of measured lesions	Censored
Treatment discontinuation for toxicity or other reason	Date of last radiological assessment of measured lesions	Censored
New anticancer treatment started	Date of last radiological assessment of measured lesions	Censored
Death before first PD assessment	Date of death	Progressed
Death between adequate assessment visits	Date of death	Progressed
Death or progression after more than one missed visit	Date of last radiological assessment of measured lesions	Censored

For the FAS population, the number of events and the PFS will be summarized by part and cohort.

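### Duration of response ends at progression only, with no rule for death or censoring, while PFS in the same SAP ends at progression or death

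*SAP*

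**What the plan says.** SAP section 6.10.2.2.3 restricts DOR to patients with CR or PR and measures it from "the first observation of response before confirmation) to the date of objectively determined PD". It says nothing about responders who die, start another anticancer treatment, miss assessments or are still in response at the cut-off.

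SAP section 6.10.2.2.2 ends PFS at "the date of objectively determined PD or death from any cause, whichever is first". That section continues "Censoring rules are described in" Table JGDK.6.1, which is invoked for PFS only. The table counts a death before the first progression assessment as an event, and likewise the row "Death between adequate assessment visits". It censors a death that follows more than one missed visit. It also censors patients who stop for undocumented progression, for toxicity or for another reason.

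On method, SAP section 6.10.2.2 says "the progression-free survival (PFS) and the duration of response (DOR) will be evaluated using the Kaplan-Meier method". On output, section 6.10.2.2.3 says "For the responders in the FAS population, the number of events and the DOR will be summarized by part and cohort". The protocol adds no definition; its section 10.6 says only "Progression-free survival and duration of response will also be included in efficacy data". Protocol section 10.1 leaves analysis detail to the SAP, so the SAP sentence is the only definition of DOR.

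**The concern.** Two time-to-event outcomes in adjacent sections end differently, and no reason is given. Because the PFS definition names death separately from objectively determined progression, the DOR wording cannot be read as covering death by implication.

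If progression is the only event, Kaplan-Meier handles a dead responder as someone whose response might still have ended later by progression. A dead patient cannot progress, and death close to clinical worsening is unlikely to be unrelated to progression, so that censoring would be informative. The same patient could be a PFS event at death and a non-event for DOR, and section 6.10.2.2 puts both outcomes in one listing.

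Deaths without objective progression are possible here. Table JGDK.6.1 provides rows for them. After the assessment before Cycle 5, protocol Attachment 1 schedules scans every 2 to 4 cycles, which at 3 weeks per cycle is 6 to 12 weeks apart. At stake is the DOR summary, not a primary conclusion.

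**Working it through.** The documents state no DOR figure, so there is nothing to reproduce. The check covers direction, the number of patients exposed, and an illustration of size.

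**1. Direction.** Kaplan-Meier multiplies factors 1 − d/n over event times, where d is the number of events and n the number at risk. If a death is recoded from event to censored on the same date, every n is unchanged and one factor below 1 is removed or moved closer to 1. The curve is therefore equal or higher at every time, never lower.

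This assumes that follow-up ends at the death date, which the SAP does not say. If the dead responder were instead censored at the last scan (the convention in Table JGDK.6.1), the curve could be lower between that scan and the death, but only if another responder progresses in that interval. Suppose n responders are at risk just after the scan, including the one who dies, k others progress before the death, and there is no other censoring. From the death date on, the curve is multiplied by (n − 1 − k)/n when death is an event and by (n − 1 − k)/(n − 1) when it is censored at the scan. The second is equal or higher.

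**2. Patients exposed.** Inputs: 6 patients per Part A cohort (protocol 10.1); three Part A cohorts (protocol 6.2), so 18 patients; doxorubicin response rate 10% to 30% (protocol 5.1), used only as a gauge.

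| | 10% | 30% |
|---|---|---|
| Expected responders per cohort, 6 × p | 0.6 | 1.8 |
| Chance of at least one per cohort, 1 − (1 − p)^6 | 47% | 88% |
| Expected responders in Part A, 18 × p | 1.8 | 5.4 |
| Chance of at least one in Part A, 1 − (1 − p)^18 | 85% | over 99% |

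**3. A small invented example.** Three responders have end dates at 4, 8 and 12 months. The median is the first time the curve is at or below 0.5.

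| Which end is a death | Curve at 4, 8, 12 with that death censored | Median |
|---|---|---|
| None, or all counted as events | 0.667, 0.333, 0 | 8 |
| The one at 4 | 1, 0.5, 0 | 8 |
| The one at 8 | 0.667, 0.667, 0 | 12 |
| The one at 12 | 0.667, 0.333, 0.333 | 8 |

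One death can move the median from 8 to 12 months or leave it unchanged, depending on where it falls.

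**4. Large-sample illustration.** Let f be the share of responses that end in death without documented progression, with constant hazards. If the total hazard is λ, the progression-or-death median is ln 2/λ and the progression-only median is ln 2/[λ(1 − f)], a ratio of 1/(1 − f). The documents do not give f. Over an assumed 5% to 30%:

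| f (assumed) | 5% | 10% | 20% | 30% |
|---|---|---|---|---|
| Ratio of medians | 1.05 | 1.11 | 1.25 | 1.43 |

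As a check at f = 20%, with hazards of 0.08 for progression and 0.02 for death, the progression-only median is ln 2/0.08 = 8.66. A simulated progression-or-death median was 6.92, and 8.66/6.92 = 1.25. These ratios show how the bias scales. They do not predict a cohort with one or two responders.

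**The case against.** The strongest reply is that the plan is silent rather than wrong, and that little depends on it. Nowhere does the SAP say that a responder who dies is censored for DOR. That is what Kaplan-Meier does when progression is the only event, but it is an inference. A sponsor could also intend a progression-only duration. This part of the objection stands as to wording. It does not remove the gap, because the stated endpoint excludes death and nothing says how death is then handled.

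A reader might infer that PFS always has an event where DOR has none. The documents do not support that. Table JGDK.6.1 also censors PFS for undocumented progression, for discontinuation due to toxicity or another reason, and for death after more than one missed visit. It gives no order of precedence between those rows and the death rows. Protocol section 8.3, which lets repeat scans be omitted when clinical progression is clear, leads mainly to undocumented progression, which PFS censors too.

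A reader might also infer that one death among two responders makes the median impossible to estimate. That depends on order. If the death comes first, the median is the later progression. If it comes last, the curve stays at exactly 0.5 and the answer depends on the software convention. With so few responders a median says little under either definition.

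Finally, the impact is small and visible. The study is uncontrolled and its sample size is not power-based. The efficacy listing in SAP 6.10.2.2 and the death listing in SAP 6.11.4 let a reader find any affected responder. All of this stands, and it limits the point to a low-cost improvement.

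**Conclusion.** The point holds in a limited form. DOR ends at objectively determined progression only and has no censoring rule, while PFS ends at progression or death. Following the DOR sentence as written, a responder's death without documented progression produces no event. The DOR curve is then equal to or higher than under progression-or-death, provided follow-up ends at the death date, and it may disagree with PFS for that patient.

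It would go too far to conclude that DOR will be overstated or that the analysis always favours the drug. If no responder dies without documented progression, the two definitions give the same result. The size cannot be derived from the documents: the ratios of 1.05 to 1.43 rest on an assumed f and constant hazards, and the three-responder example is invented. The expected 0.6 to 1.8 responders per cohort borrow the doxorubicin response rate and do not apply to Part B. No primary objective depends on DOR.

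**What to change.** In SAP section 6.10.2.2.3, define DOR as the time from the first observed CR or PR that is later confirmed to the earlier of objectively determined progression and death from any cause. Add that the censoring rules of Table JGDK.6.1 also apply to DOR. If a progression-only duration is intended, say so explicitly and state how and on what date deaths are handled.

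The cost is a few words. No new data item is needed, because overall survival (SAP 6.10.2.2.1) and the death listing (SAP 6.11.4) already use deaths. The SAP describes two Part A cohorts where the protocol has three, so the wording could go in with that update.

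Two limits remain. Patients whom the table censors for PFS would be censored for DOR as well, so the change aligns the two outcomes without capturing every death. Patients normally leave the study after the follow-up visit, set at 28 days from the last dose (protocol 8.1.2.2.3), and Attachment 1 schedules no survival visit, so later deaths may be missed under either definition. The only downside is that DOR may become slightly shorter.

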6.11. Safety Analyses

6.11.1. Extent of Exposure

The exposure data of the study drug (i.e. number of cycles, number of infusions, duration of treatment, cumulative dose, dose intensity and relative dose intensity) will be listed for the FAS population.

These data are defined as follows:

- Number of cycles = Maximum cycle given per patient
- Number of infusions for olaratumab = Total number of infusions
- Duration of treatment for olaratumab (weeks) = (Date of Day 1 of last cycle + 21 – Date of Cycle 1 Day 1) / 7
- Cumulative dose for olaratumab (mg/kg) = Sum of (total doses administered [mg] / baseline weight [kg] or available weight [kg] prior to each infusion in case of more than 10% change from baseline)
- Dose intensity for olaratumab (mg/kg/week) = (Cumulative dose for olaratumab) / (Duration of treatment for olaratumab)
- Relative dose intensity for olaratumab (%) = (Dose intensity) / (Planned weekly dose intensity) × 100,

where planned weekly dose intensity (mg/kg/week) = 15 mg/kg × 2 intravenous administrations / 3 weeks = 10 mg/kg/week.

[Part A only]

- Number of infusions for doxorubicin = Total number of infusions
- Duration of treatment for doxorubicin (weeks) = (Date of Day 1 of last cycle + 21 – Date of Cycle 1 Day 1) / 7
- Cumulative dose for doxorubicin (mg/m²) = Sum of (total doses administered [mg] / baseline body surface area [m²] or available body surface area [m²] prior to each infusion in case of more than 10% change from baseline)
- Dose intensity for doxorubicin (mg/m²/week)
- Relative dose intensity for doxorubicin (%), where planned weekly dose intensity is 25 mg/m²/week.

A listing of study drug exposures will be provided. Also, details of treatment delays, treatment omissions, treatment reductions, and treatment interruptions will be listed.

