7.2.2. Dose Adjustments and Delays

7.2.2.1. Delays and Omission

In the case that olaratumab or doxorubicin cannot be administered due to any reason including toxicity, the administration can be delayed beyond the time window within the cycle. If the planned administration cannot be conducted within the cycle, the dose is defined as an omission. For olaratumab-related toxicity \geq Grade 3 not adequately controlled with appropriate supportive care, olaratumab should not be administered until the toxicity becomes \leq Grade 2 or returns to pretreatment baseline.

Part A

Illustrative examples of dose adjustments are shown in [Attachment 5](#).

In general, discontinuation of 1 study drug (olaratumab or doxorubicin) will not necessitate discontinuation of the other study drug. Dose omission, delays, or discontinuation of olaratumab due to an olaratumab-related toxicity will not alter those of doxorubicin. Similarly, olaratumab therapy should not be altered for doxorubicin-related toxicity.

Day 1 of Cycles 2 through 7 (the first cycle of olaratumab monotherapy for the patients who receive doxorubicin on Cycle 7 or later, by reason that cumulative dose of doxorubicin does not reach 500 mg/m² during the first 6 cycles) is defined as the 21st day after the first doxorubicin administration in the previous cycle. Day 1 of Cycle 8 (the second cycle of olaratumab monotherapy for the patients who receive doxorubicin on Cycle 7 or later, by reason that cumulative dose of doxorubicin does not reach 500 mg/m² during the first 6 cycles) or any of the following cycles is defined as the 21st day after the first olaratumab administration in the previous cycle. In the case that olaratumab is delayed or omitted for any reason (including AEs), administration of doxorubicin will continue according to the original schedule. Dose delay of olaratumab on Day 8 is allowed until 7 days before Day 1 of the following cycle. Upon

resolution of the event(s) causing the delay and omission in olaratumab administration, olaratumab treatment will resume according to a Day 1/Day 8 schedule. In this study, every effort will be made to synchronize administration of olaratumab and doxorubicin according to the original dosing schedule; therefore, olaratumab may be administered for up to 4 weeks in a row.

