- a If neither olaratumab nor doxorubicin are administered on this date, Day 1 will be the next following day when either olaratumab or doxorubicin is actually administered.
- b If olaratumab is not administered on this date, Day 1 will be the next following day when olaratumab is actually administered.
- c The follow-up period starts on the day after the patient and the investigator agree to discontinue study treatment and extends 28 days (± 5 days) from the last dose of study drug (olaratumab or doxorubicin). Note (exception): For patients who discontinue from study treatment after a treatment delay, the follow-up visit can be performed after the allowed time window, if it is difficult to perform the follow-up procedures within this time period. In such a situation, the follow-up visit should be performed as early as possible.
- d No time window is allowed for Day 8 in Cycle 3.
- e Predose only.
- f Vital sign measurements will be obtained prior to each olaratumab administration.
- g Cohort 1 only.
- h When enough data for the analysis of the primary and the secondary endpoints has been collected as determined by the sponsor and the patient has continued the study treatment for more than 3 years, coagulation test and urinalysis will no longer be mandatory.

Study Schedule for Protocol I5B-JE-JGDK – Part B: Screening and Cycle 1

Relative day within a cycle	Screening			Cycle 1		Comments
	≤21	≤14	≤7	1	8	
Informed consent	X					Informed consent form signed (prior to performance of any protocol-specific tests/procedures and patients must be ≥ 20 years of age).
Medical history		X				Includes past and current medical conditions, treatments, and alcohol/tobacco use.
Pregnancy test			X			
Physical examination		X		X ^a	X ^a	Includes medical interview height (at screening only) and weight.
Vital Signs		X		X ^b	X ^b	Pulse rate, respiration rate, temperature, and supine blood pressure will be measured.
ECOG performance status		X		X ^a		
NYHA classification		X				
ECG	X			See Attachment 4		Screening ECGs will be performed locally. Obtain ECGs before any associated blood draws.
Hematology		X		X ^a	X ^a	
Serum chemistry		X		X ^a	X ^a	
Coagulation		X		X ^a		
Urinalysis		X		X ^a		
Hepatitis B and C virus	X					Includes tests for Hepatitis B surface antigen, Hepatitis B surface antibody, Hepatitis B core antibody and Hepatitis C antibody. Test for Hepatitis B DNA will be performed as necessary.
CTCAE v4.03 grading	X			X	X	

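### SAP 6.11.1 does not say whose 'last cycle' ends each drug's treatment duration, and its olaratumab planned intensity does not reflect the Cohort 3 loading cycle

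*SAP*

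**What the plan says.** SAP Section 6.11.1 defines the exposure variables. The doxorubicin line begins "Duration of treatment for doxorubicin (weeks) = (Date of Day 1 of last cycle + 21", then subtracts the date of Cycle 1 Day 1 and divides by 7. The olaratumab line has the same right-hand side. The only cycle count is "Number of cycles = Maximum cycle given per patient". Dose intensity is cumulative dose over duration (written out for olaratumab only), and RDI is dose intensity over a planned weekly figure. For olaratumab that figure is given as "where planned weekly dose intensity (mg/kg/week) = 15 mg/kg × 2 intravenous administrations / 3 weeks = 10 mg/kg/week". For doxorubicin it is 25 mg/m²/week, under a Part A label. Neither figure is limited to a cohort. The section also promises that "details of treatment delays, treatment omissions, treatment reductions, and treatment interruptions will be listed".

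The protocol provides for cycles on one drug. Section 7.2.1.2 lets olaratumab continue alone after six cycles, or after doxorubicin is stopped. It also lets doxorubicin continue if olaratumab stops during the first six. Cycle numbering carries on with olaratumab alone: Section 7.2.2.1 refers to "Day 1 of Cycle 8 (the second cycle of olaratumab monotherapy".

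SAP Section 3 ties the supplied SAP to the protocol of December 2014, and SAP Section 5.1 describes two Part A cohorts. Amendment (a) added Cohort 3, with olaratumab 20 mg/kg on Days 1 and 8 of Cycle 1 and 15 mg/kg on those days afterwards. Protocol Section 10.4 requires dose intensity and RDI summarized by part and cohort.

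**The concern.** Two programmers could both follow Section 6.11.1 and report different RDIs for the same patient. If the last cycle is the patient's, doxorubicin RDI falls because olaratumab went on, with no doxorubicin dose reduced, omitted or delayed. Longer treatment on one drug would then look like poor delivery of the other. Olaratumab is affected in the same way when doxorubicin continues alone.

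In Cohort 3, a denominator built from 15 mg/kg alone would put olaratumab RDI on a different scale from Cohorts 1 and 2, although Section 10.4 presents the cohorts together. It could also partly mask delay.

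**Working it through.** **Inputs.** Doses and the 21-day cycle come from Protocol Table JGDK.7.1. Duration, dose intensity and RDI come from SAP 6.11.1. Unless a delay is stated, the examples assume full dosing on schedule, so duration is 3 weeks per cycle.

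**The SAP's own denominators reproduce.**
- Olaratumab: 15 × 2 / 3 = 10 mg/kg/week.
- Doxorubicin, Cohort 1: 25 × 3 / 3 = 25 mg/m²/week.
- Doxorubicin, Cohorts 2 and 3: 75 / 3 = 25 mg/m²/week.

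**Doxorubicin for six full cycles, then olaratumab alone.** Cumulative doxorubicin is 6 × 75 = 450 mg/m². With the patient's last cycle k, literal RDI = 450 / (3k) / 25.

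| Patient's last cycle k | Literal | Per drug: 450 / 18 / 25 |
|---|---|---|
| 6 | 100% | 100% |
| 7 | 85.7% | 100% |
| 8 | 75% | 100% |
| 12 | 50% | 100% |
| 52 (156 weeks, about 3 years) | 11.5% | 100% |

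The last row is an illustration. Amendment (b) provides for patients treated for more than 3 years.

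**Mirror case.** Olaratumab for three full cycles (90 mg/kg), then doxorubicin alone to Cycle 6: literal 90 / 18 / 10 = 50%; per drug 90 / 9 / 10 = 100%.

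**Early stop of doxorubicin.** Four full cycles (300 mg/m²) with olaratumab to Cycle 8: literal 300 / 24 / 25 = 50%; per drug 300 / 12 / 25 = 100%. Against six planned cycles the figure is 300 / 450 = 66.7%. Which of the last two to report is a convention.

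**Cohort 3 olaratumab, fully dosed, against 10 mg/kg/week.** Cumulative dose after N cycles is 40 + 30(N−1) mg/kg.

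| N | Cumulative (mg/kg) | Planned mg/kg/week: cumulative / (3N) | RDI against 10 |
|---|---|---|---|
| 1 | 40 | 13.33 | 133.3% |
| 2 | 70 | 11.67 | 116.7% |
| 6 | 190 | 10.56 | 105.6% |

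**Does the regimen-specific denominator put the cohorts on one scale?** Take N = 4 with three weeks of total delay, so 15 weeks. Cohort 2: 120 / 15 / 10 = 80%. Cohort 3 against 10: 130 / 15 / 10 = 86.7%. Cohort 3 against its own plan: (130 / 15) / (130 / 12) = 80%.

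**How delays enter a per-drug duration.** Section 7.2.2.1 says "the administration can be delayed beyond the time window within the cycle". Up to Cycle 7, Day 1 of the next cycle is counted from the first doxorubicin dose of the current one.
- Doxorubicin slips to Day 15 in Cycle 5: Cycle 6 starts 84 + 35 = 119 days after Cycle 1 Day 1. Duration is (119 + 21) / 7 = 20 weeks and RDI is 450 / 20 / 25 = 90%.
- The same slip in Cycle 6, the last doxorubicin cycle, with olaratumab on time: (105 + 21) / 7 = 18 weeks, 100%.
- Both drugs one week late at Cycle 6: by Attachment 1, for Cycles 2 to 6, "Day 1 will be the next following day when either olaratumab or doxorubicin is actually administered", so Day 1 moves. (112 + 21) / 7 = 19 weeks and 450 / 19 / 25 = 94.7%.

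From Cycle 7 on, olaratumab sets Day 1: "If olaratumab is not administered on this date, Day 1 will be the next following day when olaratumab is actually administered".

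**The case against.** The strongest reply is that the section already means per drug. It names the drug on the left of each line and does not repeat it on the right. The number of infusions for each drug is simply a total, and nobody would pool the two drugs there. A separate doxorubicin line would be redundant if one patient-level duration were meant. The per-patient cycle count is the one line without a drug label, so it is weak evidence for the labelled lines. This stands: the per-drug reading is at least as natural. A reader might infer that the SAP's formula is wrong or that RDI will be miscalculated. The text does not support that. It shows an ambiguity, and the diluted figures depend on the literal reading.

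A reader might also infer that the SAP has no RDI denominator for Cohort 3 at all. That is not so. The doxorubicin figure is stated for Part A without a cohort limit and fits exactly (75 / 3 = 25). The olaratumab figure also has no cohort limit; it just does not reflect the loading cycle.

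Nor was it an error for this SAP to cover two cohorts. It was approved on 04-Mar-2015, before Amendment (a) of 26 Jun 2015. The documents do not show whether a later SAP exists, and the Cohort 3 percentages assume an unchanged carry-over that nothing states.

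Finally, cumulative dose, infusions and dose changes are listed as well, so dilution could be detected by anyone who looked.

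**Conclusion.** The point holds as a minor clarification in two parts. First, 'last cycle' needs to be tied to the named drug. Under the literal reading, doxorubicin RDI for six full cycles would be 85.7%, 75% or 50% with olaratumab to Cycle 7, 8 or 12, instead of 100%, on the assumption of full, undelayed dosing. Second, 10 mg/kg/week is correct for Cohorts 1 and 2 and Part B but does not describe the Cohort 3 plan. The mismatch is largest after one cycle (133.3%) and shrinks to 105.6% by six.

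It would be tempting to read this as a threat to the tolerability conclusion. It is not. Protocol Section 7.2.1.5 judges tolerability on DLT counts in Cycle 1, and the sample size does not rest on exposure. Only descriptive exposure data are affected.

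**What to change.** In SAP 6.11.1:

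1. Define duration for each drug as (Day 1 of the last cycle in which that drug was given + 21 − Cycle 1 Day 1) / 7.
2. Add, for each drug, the number of cycles in which it was given.
3. For Cohort 3, set planned olaratumab intensity to [40 + 30(N−1)] / (3N) mg/kg/week, with N the last olaratumab cycle. Keep 10 mg/kg/week for Cohorts 1 and 2 and Part B, and 25 mg/m²/week for doxorubicin in all Part A cohorts.
4. State that this RDI describes delivery while on that drug, so early discontinuation is read from the per-drug cycle count and cumulative dose.
5. State that a delay in a drug's final cycle lowers RDI only if Day 1 of that cycle moves. Other final-cycle delays must be read from the delay listing.

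The cost is SAP wording and minor programming, with no new data.

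A separate matter: Table JGDK.7.1 footnote b and Section 7.2.1.2 differ on when doxorubicin may be given after Cycle 6. The footnote lets treatment run to the later of six cycles and 500 mg/m². The section allows it for patients who fell short because of reductions or omissions. The two should be reconciled.

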7.2.1.1. Olaratumab

With the exception of the 20 mg/kg loading dose of olaratumab on Days 1 and 8 in Cycle 1 of Cohort 3, all patients will receive 15 mg/kg of olaratumab on Days 1 and 8 of each 21 day treatment cycle, administered as an intravenous infusion over approximately 60 minutes, until progressive disease or meeting the other discontinuation criteria. Patients enrolled in Part A can be hospitalized for the first 8 days in Cycle 1, according to routine institutional practice.

The dose of olaratumab is dependent upon the patient's weight in kilograms. A change of weight $\geq 10\%$ (increase or decrease) from baseline will result in re-calculation of olaratumab dose to be administered.

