7.2.1.2. Doxorubicin

In Part A only, all patients will receive 25 mg/m² of doxorubicin on Day 1/2/3 (Cohort 1) or 75 mg/m² of doxorubicin on Day 1 (Cohort 2 and 3) of each 21-day cycle, administered as an intravenous infusion over approximately 30 minutes. Doxorubicin will be administered for up to 6 cycles until progressive disease or meeting the other discontinuation criteria. For patients whose cumulative dose of doxorubicin does not reach 500 mg/m² during the first 6 cycles (because of dose reductions or omissions), doxorubicin can be administered up to 500 mg/m² at the following cycles at the discretion of the investigator. On the days when both olaratumab and

doxorubicin are administered, doxorubicin will be administered approximately 1 hour after the completion of the olaratumab infusion.

If a patient completes 6 cycles, olaratumab monotherapy can be continued in the absence of disease progression or other discontinuation criteria.

If doxorubicin is discontinued (eg, for reasons of toxicity), olaratumab monotherapy can be continued. For patients who discontinue olaratumab during the first 6 cycles of treatment, doxorubicin may be continued (for up to 6 cycles or up to 500 mg/m² at the discretion of the investigator).

The dose of doxorubicin will be calculated using body surface area and is dependent upon the patient's baseline height in centimeters. A change of weight $\geq 10\%$ from baseline will result in re-calculation of doxorubicin dose to be administered based on body surface area.

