6.7. Patient Characteristics

For the FAS population, demographic and baseline disease characteristics will be summarized by part and cohort.

Demographic characteristics are as follows:

age (years), age categories (<65 years vs. ≥65 years), gender, race, height (cm), weight (kg), body surface area (m²) and Body Mass Index (kg/m²),

where body surface area is calculated using DuBois method; $0.007184 \times \text{weight}^{0.425} \times \text{height}^{0.725}$ and Body Mass Index = $\text{weight} / (\text{height} / 100)^2$.

Baseline disease characteristics are as follows:

Alcohol use, Tobacco use, Eastern Cooperative Oncology Group (ECOG) performance status, initial pathological diagnosis (or cancer type), disease stage at diagnosis, TNM at diagnosis, sites of Metastatic Disease, and duration of disease (months from the first confirmation of cancer to the first infusion)

In addition, prior anticancer treatments or surgery (radiotherapy, surgical procedure and systemic therapy), historical conditions and pre-existing conditions will be summarized by part and cohort.

Listings of demographic and baseline disease characteristics, of historical conditions and of pre-existing conditions also will be provided for the FAS population.

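### SAP 6.11.1 appears to switch the doxorubicin denominator on a body surface area change, but the protocol re-doses on weight, so exposure can be misstated by 4% to 10% per affected infusion

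*SAP*

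**What the plan says.** **Dosing.** Protocol 7.2.1.2 says the doxorubicin dose is calculated from BSA and "is dependent upon the patient's baseline height in centimeters". A weight change of 10% or more "from baseline will result in re-calculation of doxorubicin dose to be administered based on body surface area". For olaratumab, protocol 7.2.1.1 applies the same threshold: a weight change of 10% or more, in either direction, "from baseline will result in re-calculation of olaratumab dose to be administered".

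**Analysis.** SAP 6.11.1 builds cumulative doxorubicin dose (mg/m²) by dividing the milligrams given by baseline BSA, or by "available body surface area [m²] prior to each infusion in case of more than 10% change from baseline". The olaratumab line has the same form, with weight in place of BSA. Dose intensity is cumulative dose over weeks of treatment. Relative dose intensity (RDI) compares it with the plan; for doxorubicin the "planned weekly dose intensity is 25 mg/m²/week".

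**BSA formula.** SAP 6.7 says that "body surface area is calculated using DuBois method", with weight raised to the power 0.425 and height to the power 0.725.

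**The concern.** The two documents seem to attach the same 10% to different quantities: weight in the protocol, BSA in the SAP. BSA responds weakly to weight, so the protocol's trigger is reached long before a 10% change in BSA. Between the two thresholds the milligrams follow the new BSA while the analysis still divides by the old one.

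The resulting error has a direction. A patient dosed exactly to plan looks under-dosed after weight loss and over-dosed after weight gain. Protocol 10.4 names cumulative dose, dose intensity and RDI among the safety variables for Part A. With about six patients per cohort, one affected patient is visible in the listing and can move a cohort summary.

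**Working it through.** **Inputs**
- Re-dosing trigger: weight change of 10% or more (protocol 7.2.1.2).
- Height fixed at baseline, so BSA changes only through weight (protocol 7.2.1.2).
- Weight exponent of BSA: 0.425 (SAP 6.7).
- SAP trigger, read literally: BSA change of more than 10% (SAP 6.11.1).
- Planned doxorubicin: 75 mg/m² per 21-day cycle, in Cohort 1 as 3 × 25 mg/m² (protocol 6.2).

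**Step 1: reproduce the SAP's planned dose intensity.** 75 / 3 weeks = 25 mg/m²/week, and 3 × 25 / 3 = 25 for Cohort 1. This agrees with SAP 6.11.1. Six on-time cycles last 18 weeks and total 6 × 75 = 450 mg/m², so RDI = (450 / 18) / 25 = 100%.

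**Step 2: effect of a 10% weight change on BSA.** With height fixed, BSA ratio = (weight ratio)^0.425.
- 10% loss: 0.90^0.425 = 0.956, a fall of 4.4%.
- 10% gain: 1.10^0.425 = 1.041, a rise of 4.1%.

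**Step 3: weight change needed for a 10% BSA change.**
- Loss: 0.90^(1/0.425) = 0.780, about 22.0%.
- Gain: 1.10^(1/0.425) = 1.251, about 25.1%.

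The affected range is therefore a loss of 10% to about 22% or a gain of 10% to about 25%. Beyond it, the SAP does switch to current BSA. Below 10%, dose and denominator both rest on baseline, so they agree.

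**Step 4: what one full dose is recorded as.** Recorded dose = 75 × BSA ratio. It runs from 71.7 down to 75 × 0.90 = 67.5 for losses, and from 78.1 up to 75 × 1.10 = 82.5 for gains. The error is 4% to 10% per infusion.

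**Step 5: six full, on-time cycles, re-dosed from Cycle 2.** Recorded total = 75 + 5 × 75 × BSA ratio; RDI = total / 450.

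| Weight change | BSA ratio | Recorded total (true 450) | RDI (true 100%) |
|---|---|---|---|
| 10% loss | 0.956 | 433.6 | 96.4% |
| 15% loss | 0.933 | 425.0 | 94.4% |
| 20% loss | 0.910 | 416.1 | 92.5% |
| 10% gain | 1.041 | 465.5 | 103.4% |
| 20% gain | 1.081 | 480.2 | 106.7% |

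At the edges of the range the error is at most about 37 mg/m² (5 × 75 × 0.10 = 37.5), with RDI about 92% or 108%. Later re-dosing shrinks it: a 10% loss from Cycle 4 gives 440.1 and 97.8%.

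**Step 6: sensitivity to the BSA formula.** The SAP gives DuBois for baseline characteristics, and the formula used at sites is not stated. Assuming a weight exponent anywhere from 0.425 to 0.55, a 10% weight change moves BSA by 4.1% to 5.6%. The SAP trigger then needs a loss of 17.4% to 22.0% or a gain of 18.9% to 25.1%. The gap remains.

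**Step 7: the other reading.** If the SAP's 10% means weight, the only difference left is more than 10% (SAP) against 10% or more (protocol). It applies only to a patient at exactly 10%. The olaratumab line differs from the protocol only in this way.

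**The case against.** The best reply is that the SAP never says a 10% change in BSA. It says a change of more than 10% and gives that change no subject. Ten percent of weight is the protocol's re-dosing threshold for both drugs, so the phrase may be that rule carried over from the olaratumab line. This stands as a possibility, so the mismatch cannot be asserted as the sponsor's intent. It does not make the text safe: BSA is the only quantity the sentence names, and a programmer following it would compare BSA values.

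A reader might also infer more than the documents support:

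- **That exposure is wrong for every re-dosed patient.** It is not. Beyond about 22% loss or 25% gain the rule uses current BSA.
- **That a true 500 mg/m² could appear as 467 or 531 after a 15% change.** This needs every dose, including the first, to be given at the changed weight (500 × 0.933 or 500 × 1.061). SAP 6.1.2 defines baseline as the last value before the first infusion, so the first dose is given at about baseline weight. With only the first 75 mg/m² given there, the figures are about 472 and 526, and six full cycles total 450, not 500.
- **That the primary assessment is compromised.** Tolerability rests on Cycle 1 dose-limiting toxicity (protocol 7.2.1.3 and 7.2.1.5). Doxorubicin in Cycle 1 is given on Days 1 to 3 at most, before a 10% weight change would normally arise.
- **That a planned cardiotoxicity analysis is distorted.** The SAP plans none against cumulative dose; echocardiography results are listed. Nothing says the SAP derivation is used to apply the 500 mg/m² figure during treatment.

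SAP 6.11.1 also lists dose reductions separately, so an RDI of 96% with no recorded reduction could be recognised as an artefact. That lessens the point but does not remove it, because protocol 10.4 has exposure summarized as well.

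**Conclusion.** The point holds on the literal reading. SAP 6.11.1 leaves the subject of its 10% change unstated; taken as BSA, it misstates recorded doxorubicin by 4% to 10% for each affected infusion. With re-dosing from Cycle 2, the error over six full cycles is at most about 37 mg/m², or about 8 percentage points of RDI.

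These figures assume full planned doses on schedule, a constant weight after the change, fixed height and the DuBois exponent. On the weight reading, the defect shrinks to patients at exactly 10%. The documents give no rate of weight change of this size, so the number affected among about 18 planned Part A patients (three cohorts of six) is unknown and could be zero.

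The consequence is confined to exposure listings and summaries. Sample size, cohort decisions and efficacy results are unchanged. It should be corrected because the rule, followed as written, can report a wrong figure for a patient dosed to plan.

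**What to change.** In SAP 6.11.1, divide each administered dose by the BSA (doxorubicin) or weight (olaratumab) actually used to calculate that dose, and sum the results.

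If a trigger is kept, state it for both drugs as a weight change of 10% or more from baseline, to match the protocol. This is second best: weight can drift after a recalculation, so the BSA available before a later infusion need not be the one behind the dose.

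The cost is about one sentence and a small programming change. Attachment 1 of the protocol already collects weight and BSA at Part A physical examinations. If the BSA used for each dose is not itself recorded, it would have to be reconstructed from those values, and the SAP should say how. Protocol 10.1 allows an analysis change that does not alter a principal feature to be described and justified in the study report without an amendment. The change concerns the derivation of exposure only and alters no dosing rule.
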